In Part D, participants will return to the study site for on-treatment evaluations on Day 1 and at Weeks 2, 4, 8, 12, 14, 20, 24, 26, and every 8 weeks after Week 24 until the last participant enrolled in Part D has completed this Week 24 visit. At this time, all participants will be contacted to return and complete the Final On-Treatment Visit (see Schedule of Events in [Appendix 2](#)). Blood and urine specimens for safety laboratory assessments will be collected after at least an 8-hour fast. A final study visit will be conducted 2 weeks \pm 3 days after the last dose of study drug (Week 14 \pm 3 days for Parts B and C; 2 weeks after the final On-Treatment Visit [\pm 3 days] for Part D), when participants will undergo a final [REDACTED] measurement, as well as follow-up end of study (EoS) evaluations.

Participants who discontinue study drug for safety reasons prior to completion of 12 weeks (Parts B and C) or at least 24 weeks (Part D) of treatment will be asked to remain in the study to complete all remaining assessments; if this is not feasible, they will be asked to return to the clinic for an Early Termination (ET) visit for follow-up evaluations.

[REDACTED] measurements will be obtained via spirometry and will be performed using study-standardized equipment and according to international guidelines (American Thoracic Society [ATS]/ European Respiratory Society [ERS]/ Japanese Respiratory Society [JRS]/ Latin American Respiratory Society [ALAT]). Spirometry reading will be centralized.

[REDACTED]
[REDACTED]
The DSMB will assess participant safety at predetermined intervals during the study, including prior to initiating Part D and following the enrollment of the last participant in Part D. [REDACTED]
[REDACTED]

The total number of participants enrolled in Parts B, C, and D of the study will be approximately 112, with approximately 84 receiving PLN-74809 and 28 receiving placebo.

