3.2 Rationale for PLN-74809 Doses and Control Group

This study will be the first to characterize the safety, tolerability and PK of PLN-74809 in participants with IPF, with or without co-administration with SoC (pirfenidone or

nintedanib). The proposed randomized, double-blind study design allows a reduction in bias in the assessment of drug safety and tolerability. Stratification for background treatment with SoC will ensure a similar proportion of participants in each treatment group. The proposed sample size and 12-week treatment duration of Parts B and C are expected to provide meaningful PK information in the IPF population, as well as allow for preliminary evaluation of dose-dependent treatment effects on [REDACTED] study endpoints, comparing PLN-74809 to placebo.

The evaluation of PLN-74809 40 mg in Part B of this study is supported by the 13-week toxicology data, safety and PK data at these doses from study [REDACTED], as well as the PD findings from study [REDACTED], where this dose led to reduction of TGF- β activation in the lungs of healthy participants following 7 days of dosing, as assessed by reduction in phosphorylated SMAD2 (pSMAD2)/SMAD2 ratio in BALF (See PLN-74809 Investigator's Brochure for more details).

The evaluation of PLN-74809 80 mg and 160 mg doses in Part C is supported by all available safety and PK data from Parts A and B, as well as safety and PK data evaluating higher doses (80 and 160 mg) from study [REDACTED].

The evaluation of PLN-74809 320 mg in Part D is supported by all available safety and PK data from Parts B and C, as well as safety and PK data evaluating the higher dose (320 mg) from study [REDACTED].

In Study [REDACTED], PLN-74809 showed a favorable safety and tolerability profile in healthy participants after single doses of up to [REDACTED] mg and after 7 days of treatment at doses of up to [REDACTED] mg (Section 1.1.2). The safety margins determined after single doses of [REDACTED] mg and multiple doses of [REDACTED] mg were calculated using the NOAEL observed in toxicology studies in [REDACTED] for both area under the plasma concentration-time curve from time zero to 24 hours (AUC_{0-24}) and C_{max} for the measured [REDACTED] of PLN-74809. At all dose levels studied, there was a [REDACTED] between the unbound AUC_{0-24} and [REDACTED] no observed adverse effect level (NOAEL). See the PLN-74809 Investigator's Brochure for more details.

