6.4 Method of Assigning Participants to Treatment Groups

Up to approximately 112 participants may be enrolled in study Parts B (n = 28), C (n = 56) and D (n = 28). The randomization for each of the dose cohorts in Parts B, C, and D will be 3:1 (active:placebo). Randomization will be stratified by use of SoC IPF therapy (pirfenidone or nintedanib) (SoC use; yes or no).

- In Part B, 28 eligible participants were randomized on Day 1 (Visit 2) in a 3:1 ratio (40 mg PLN-74809:placebo).
- In Part C, 56 eligible participants will be randomized on Day 1 (Visit 2) in a 3:3:2 ratio (80 mg PLN-74809:160 mg PLN-74809:placebo).
- In Part D, 28 eligible participants will be randomized on Day 1 (Visit 2) in a 3:1 ratio (320 mg PLN-74809:placebo).

Assignment will be performed in a blinded manner using interactive response technology (IRT) based on a previously generated randomization code. Randomization will occur immediately prior to dosing on the morning of the first dose (Day 1).

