This document is the property of [REDACTED] and may not be duplicated, copied, altered or removed from company without prior approval from [REDACTED] or in compliance with [REDACTED].

Controlled Quality Management Document		
	Sponsor:	Pliant Therapeutics Inc.
	Protocol Number:	PLN-74809-IPF-202
STATISTICAL ANALYSIS PLAN. PHASE 2-3-4		

SAP Amendments Post Database Lock for Parts A/B/C Week 12 and pre database lock for Part D Week 12

Version	Issue Date	Section	Revision / Addition
Addendum 1.0	02 Dec 2022	6.15.2	CTCAE grading for laboratory test parameters removed
		6.11.1	Added new pooled placebo groups and Wilcoxon rank sum test for FVC at Week 12
		7	Added text to clarify data cut off day for Part D interim
		11	List of Tables, Figures and Listings was updated.
Addendum 2.0	06 Dec 2022	11	List of Tables, Figures and Listings was updated.
Addendum 3.0	12 Dec 2022	11	List of Tables, Figures and Listings was updated.

SAP Amendments Post Database Lock for Parts A/B/C/D Week 12 and pre database lock for Part D Week 24

Version	Issue Date	Section	Revision / Addition
Addendum 4.0	31 Jan 2023		
		6.2.20	Addition of SAS code to determine outliers
		11	List of Tables, Figures and Listings was updated.
Addendum 5.0	30 Mar 2023	6.6	Added summary of pulmonary function at baseline
		11	List of Tables, Figures and Listings was updated.

SAP Amendments Post Final Database Lock

Version	Issue Date	Section	Revision / Addition
Post database lock	09 May 2023	6.6	Added baseline summaries by study part
		11	List of Tables, Figures and Listings was updated.

Confidentiality Statement
This document is the property of [REDACTED] and may not be duplicated, copied, altered or removed from company without prior approval from [REDACTED] or in compliance with [REDACTED].

Table of Contents

1	INTRODUCTION	7
2	STUDY OBJECTIVES	7
2.1	Primary Objective	7
2.2	Secondary Objective	7
2.3	Exploratory Objectives	7
3	ENDPOINTS	8
3.1	Primary Safety Endpoint.....	8
3.2	Secondary Pharmacokinetic Endpoints.....	8
3.3	Secondary Pharmacodynamic Endpoints.....	8
3.4	Exploratory Endpoints	8
3.4.1	Exploratory Efficacy Endpoints.....	8
3.4.2	Other Assessments or Analyses	9
4	SAMPLE SIZE	9
5	RANDOMIZATION	9
6	PLANNED ANALYSES.....	10
6.1	Analysis Populations.....	10
6.1.1	Screened Participants	10
6.1.2	Randomized Participants	10
6.1.3	Safety Population	10
6.1.4	PK Analysis Population	10
6.1.5	PD Analysis Population	11
6.1.6	Efficacy Intent-to-Treat Population	11

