6.3.6 Data Displays

All clinical data tabulations, figures and listings will be generated as individual Rich Text Format (.rtf) files using [REDACTED]¹. Data summaries and graphical analyses will be reported within Section 14 of the CSR and individual participant data listings within Appendix 16.2 of the CSR.

Participant disposition, baseline characteristics, demographic, compliance, concomitant medication, and adverse event data will be presented by treatment group and overall. Other safety data will be presented by treatment group only.

Please note: Data from study Part A will be listed only.

Treatment group labels will be displayed as follows:

PLN-74809	PLN-74809	PLN-74809	PLN-74809	All	
(40 mg)	(80 mg)	(160 mg)	(320 mg)	PLN-74809	Placebo
(N=XX)	(N=XX)	(N=XX)	(N=XX)	(N=XX)	(N=XX)

QMD [REDACTED]	[REDACTED]
Confidentiality Statement	
This document is the property of [REDACTED] and may not be duplicated, copied, altered or removed from company without prior approval from [REDACTED] or in compliance with [REDACTED].	

[REDACTED]

Controlled Quality Management Document		
	Sponsor:	Pliant Therapeutics Inc.
	Protocol Number:	PLN-74809-IPF-202
STATISTICAL ANALYSIS PLAN. PHASE 2-3-4		

Listings will be sorted in the following order, study part (Parts B/C/D/A), treatment group, participant number, parameter, and visit unless otherwise stated. All data will be listed, participants who were not randomized will be displayed after the randomized treatment groups.

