6.6 Baseline Comparability

Comparability of treatment groups with respect to participant demographics and baseline characteristics will be assessed in a descriptive manner, but no formal statistical testing will be performed.

Baseline summaries will be presented by treatment group and overall, for the following variables based on the Safety Population:

Demographic Data

- Age at Informed Consent (years)
- Sex
- Ethnicity

Confidentiality Statement	
This document is the property of [REDACTED] and may not be duplicated, copied, altered or removed from company without prior approval from [REDACTED] or in compliance with [REDACTED].	

[REDACTED]

Controlled Quality Management Document		
	Sponsor:	Pliant Therapeutics Inc.
	Protocol Number:	PLN-74809-IPF-202
STATISTICAL ANALYSIS PLAN. PHASE 2-3-4		

- Race, where more than one race is selected the participant will be presented under the ‘Multiple races’ category in the summary but each selected race will be identified in the listing.

Baseline Characteristics

- Weight at Screening (kg)
- Height at Screening (cm)
- BMI at Screening (kg/m²)
- Fertility Status (Childbearing Potential, Postmenopausal, Surgically Sterile)
- Participant taking nintedanib or pirfenidone at Screening

Clinical Characteristics

- Pulmonary Function at Screening
- Pulmonary Function at Baseline
- DLCO Lung Function Assessment at Screening (if repeated, the last non-missing value before first dose will be taken)
- GAP Index Score and Staging
- Duration Since Diagnosis at Screening (first date reported for Idiopathic Pulmonary Fibrosis, Pulmonary Fibrosis or Interstitial Lung Disease)
- Duration of Standard of Care at Randomization (defined as the number of months from start date of nintedanib or pirfenidone to date of randomization)

Additional summaries will be completed for Part D only participants as well as placebo participants by study part.

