Spirometry parameters to be summarized by treatment group and visit include:

- FVC (mL) Actual
- % FVC Predicted
- [REDACTED]
- [REDACTED]

Confidentiality Statement	
This document is the property of [REDACTED] and may not be duplicated, copied, altered or removed from company without prior approval from [REDACTED] or in compliance with [REDACTED].	

Controlled Quality Management Document		
	Sponsor:	Pliant Therapeutics Inc.
	Protocol Number:	PLN-74809-IPF-202
STATISTICAL ANALYSIS PLAN. PHASE 2-3-4		

█ [REDACTED]

█ [REDACTED]

All spirometry data will be listed.

Sensitivity Analyses:

The MMRM will be repeated in the █ [REDACTED] █ [REDACTED] as sensitivity analyses. In addition, a sensitivity analysis will be conducted using the █ [REDACTED] █ [REDACTED]

A trimmed mean analysis trimming the participants █ [REDACTED] █ [REDACTED] will also be conducted for Part D participants.

In addition, FVC will be summarized using descriptive statistics by the following treatment groups at baseline and Week 12 for the Efficacy Intent-to-Treat Population:

- █ [REDACTED] █ [REDACTED]
- █ [REDACTED] █ [REDACTED]
- █ [REDACTED] █ [REDACTED]

Actual values, the changes from baseline and the percent changes from baseline will be presented along with 95% confidence intervals (CI) for the mean changes and mean percent change from baseline.

The two comparisons below will be performed via the MMRM on (a) FVC change from baseline at each visit, and (b) FVC percent change from baseline at each visit. Additionally, █ [REDACTED] █ [REDACTED] will test (a) FVC Week 12 change from baseline endpoint, and (b) FVC week 12 percent change from baseline :

- █ [REDACTED] █ [REDACTED]
- █ [REDACTED] █ [REDACTED]

As a further exploratory analysis, █ [REDACTED] will be utilized to analyze the change from baseline to Week 12 in FVC between subjects in each of the treatment group selections above, as well as in Part D alone (not pooled).

█ [REDACTED]	█ [REDACTED]
█ [REDACTED]	
█ [REDACTED] █ [REDACTED] █ [REDACTED] █ [REDACTED]	
█ [REDACTED]	█ [REDACTED]

Controlled Quality Management Document		
	Sponsor:	Pliant Therapeutics Inc.
	Protocol Number:	PLN-74809-IPF-202
STATISTICAL ANALYSIS PLAN. PHASE 2-3-4		

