7 INTERIM ANALYSIS

Interim analyses will be conducted at the following milestones:

- Upon completion of Parts B and C (following full enrollment and 12-week treatment duration with 40, 80, or 160 mg PLN-74809).
- Upon completion of 12-week treatment duration with 320 mg PLN-74809 in Part D.

A database freeze will occur upon completion of study Part C by the last participant. All data for study part A, B and C will be 100% cleaned and signed off by the investigators. After database freeze, participants will be unblinded and these data will be used for the statistical analysis and reporting of Parts A, B and C.

Blinding measures for interim analyses performed on data up to Week 12 for all participants in Part D will be described in a separate blinding plan.

Interim data from Part D will include all assessments up to the Week 12 assessments, [REDACTED] Adverse events or concomitant medications started/initiated post Day [REDACTED] will not be summarized in the in the interim analysis and will be presented in the final analysis. Participants who discontinue treatment or the study post the Week 12 assessment date up to Day [REDACTED] will be summarized as on treatment/on study for the purposes of the interim analyses.

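### Each dose was randomized in only one of three consecutive Parts but is compared with placebo pooled over all three, so a Part difference could be read as a dose effect

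*Protocol*

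**What the plan says.** Protocol 3.1 opens Part C only after DSMB review of the 40 mg data, and Part D only after DSMB review of Part C. Protocol 6.4 and SAP 5 randomize within each Part, stratified by SoC use (yes or no). Protocol 3.2 then says of the study as a whole: "Stratification for background treatment with SoC will ensure a similar proportion of participants in each treatment group".

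SAP 6 analyses Parts B, C and D together. SAP 6.3.6, under "Treatment group labels will be displayed as follows", lists 40, 80, 160 and 320 mg, all PLN-74809, and a single Placebo column. The FVC MMRM (SAP 6.11.1) and the biomarker MMRM (SAP 6.13) give differences from placebo with p-values. Cough (6.11.1, Patient-Reported Cough) and adverse events (6.15.1) are tabulated by treatment group.

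The SAP amendment log for Addendum 1.0, dated 02 Dec 2022, reads: "Added new pooled placebo groups and Wilcoxon rank sum test for FVC at Week 12". Its heading places it after the Parts A/B/C Week 12 lock and before the Part D Week 12 lock. On Parts A, B and C, SAP 7 says: "After database freeze, participants will be unblinded and these data will be used for the statistical analysis".

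Some analyses do separate the Parts. SAP 6.11.1 includes a further exploratory Week 12 FVC analysis in Part D alone, a trimmed-mean analysis for Part D participants, and an FVC increase/decrease summary for Part D at Weeks 12 and 24. SAP 6.6 says: "Additional summaries will be completed for Part D only participants as well as placebo participants by study part".

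**The concern.** Because each dose exists in only one Part, dose and Part are confounded once placebo is pooled. Randomization protects a dose against the placebo of its own Part. It gives no such protection against placebo participants from another Part, who enrolled in a different period and, for Part D against Parts B and C, with a different unit strength (80 mg against 40 mg, Protocol 5.1.1). Nothing in the design fixes the SoC share across Parts, so the Protocol 3.2 statement does not carry over to pooled comparisons.

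This matters because Protocol 3.2 expects a preliminary look at dose-dependent effects and says the findings will inform dose selection. A difference between Parts in case mix or SoC share could appear as a step in the dose response. The exposed results are Week 12 FVC and biomarkers, and the descriptive cough and adverse event tables. Unequal length of follow-up is a separate matter and is not counted here.

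**Working it through.** **1. The plan's own totals.** Part sizes and ratios are from Protocol 6.4. Number per arm = Part size × arm's share of the ratio.

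| Part | Size and ratio | Active | Placebo |
|---|---|---|---|
| B | 28, 3:1 | 21 (40 mg) | 7 |
| C | 56, 3:3:2 | 21 (80 mg) + 21 (160 mg) | 14 |
| D | 28, 3:1 | 21 (320 mg) | 7 |
| Total | 112 | 84 | 28 |

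This reproduces Protocol 3.1: "approximately 112, with approximately 84 receiving PLN-74809 and 28 receiving placebo".

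**2. Non-concurrent share of the pooled control.** Share = 1 − (placebo in the dose's own Part) / (placebo in all Parts).

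- 40 mg: 1 − 7/28 = 75%
- 80 and 160 mg: 1 − 14/28 = 50%
- 320 mg: 1 − 7/28 = 75%

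Protocol 3.1 gives 29 randomized in Part B, while Protocol 6.4 and SAP 5 give 28. If Part B had 8 on placebo (29 in all), the shares are 21/29 = 72%, 15/29 = 52% and 22/29 = 76%. At the first interim (Parts B and C, 21 placebo) they are 14/21 = 67% for 40 mg and 7/21 = 33% for 80 and 160 mg.

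**3. What a Part shift would do (illustration).** Assume no drug effect, no covariates, and a shift of d SD shared by everyone in Part D.

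- Pooled placebo mean: (7/28)d = 0.25d
- 320 mg minus pooled placebo: d − 0.25d = 0.75d
- Each lower dose minus pooled placebo: −0.25d
- 320 mg minus Part D placebo: 0

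At d = 0.25, the 320 mg difference is biased by 0.75 × 0.25 = 0.19 SD and each lower dose by −0.06 SD. The gap between 320 mg and the lower doses is the full 0.25 SD. The documents give no value for d.

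**4. Precision.** SE = SD × √(1/n active + 1/n placebo).

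- Pooled: √(1/21 + 1/28) = 0.289
- Own Part, 40 or 320 mg: √(1/21 + 1/7) = 0.436, ratio 1.51
- Own Part, 80 or 160 mg: √(1/21 + 1/14) = 0.345, ratio 1.20

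**5. Bias against variance for 320 mg at d = 0.25.** Root mean squared error (RMSE) with pooled placebo is √(0.1875² + 0.289²) = 0.34 SD. With Part D placebo alone it is 0.44 SD. The two are equal when 0.75d = √(0.436² − 0.289²) = 0.327, that is, d of about 0.44.

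**6. Timing of the added pools.** Parts B and C hold 7 + 14 = 21 of the 28 planned placebo participants. On the sequence in SAP 7 and the amendment log, their Week 12 results were available when Addendum 1.0 was written. The Part D Week 12 data were not yet locked. The composition of the added pools is redacted.

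**The case against.** The strongest reply is that this is a descriptive Phase 2a safety study. Protocol 12.1 says no hypothesis is tested, and seven placebo participants are too few to carry a comparison. Step 5 supports this in part: at a shift of 0.25 SD the pooled estimate has the smaller mean squared error. A reader might infer that Part D placebo should therefore be the sole reference for 320 mg. The documents do not support that, because the choice is a trade-off between bias and variance. Nor should the point be put as a type I error violation.

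Several mitigations also stand. Eligibility is common to the Parts, and Protocol 3.1 requires standardized spirometry equipment with central reading. Adverse event tables are split by SoC (SAP 6.15.1). SAP 6.6 would expose a baseline difference between Parts, although its by-Part summaries were added only after final database lock. A reader might take the Part D alone analysis to be the only concurrent comparison for 320 mg. It is not: there are the other Part D FVC analyses, and after Week 12 only Part D has on-treatment placebo data, so those comparisons are concurrent in effect.

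A reader might also infer that a Part shift passes straight into the modelled FVC and biomarker differences. The model terms are redacted, so adjustment for Part or SoC can be neither confirmed nor excluded. Such terms would not reach the descriptive tables, and cough has no model at all.

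What remains is that no visible text puts own-Part placebo beside pooled placebo for cough, biomarkers or adverse events to Week 12.

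**Conclusion.** The point holds as a risk to interpretation. On planned numbers, 75% of the pooled control is non-concurrent for 40 mg and 320 mg and 50% for 80 and 160 mg. The Part B discrepancy moves these by less than 3 points. The Protocol 3.2 sentence is too broad: SoC balance is to be expected within a Part, and pooled comparisons do not inherit it.

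The 0.19 SD bias rests on an assumed 0.25 SD Part D shift, with no drug effect and no covariates. No document reports that any shift occurred.

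On the added pools, a reader might infer that they were chosen to suit known results. The documents show only the order of events: the pools were defined after the Parts A/B/C lock, when SAP 7 has those Parts unblinded, and before the Part D Week 12 lock. The amendment log shows the lock sequence openly. SAP 9 lists the change without its timing.

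**What to change.** 1. In SAP 6.11.1 and 6.13, and in the cough and adverse event tables, show each dose to Week 12 against its own Part's placebo beside the pooled-placebo result. Present this as a consistency check, with neither made the sole reference. For Week 12 FVC at 320 mg this is already partly planned.
2. In SAP 9 and the report, state that the pooled placebo groups in Addendum 1.0 were defined after unblinding of Parts A/B/C and before the Part D Week 12 lock.
3. Restate Protocol 3.2: SoC balance is expected within each Part only.

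The cost is a few more columns and some wording. The downside is imprecision: the own-Part interval for 320 mg is about 1.5 times as wide (SE 0.44 against 0.29 SD). Agreement between the two results should therefore be read loosely.

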3.3 Study Duration

The duration for Parts B and C of the study will be up to 18 weeks each (up to 4 weeks of screening, 12 weeks of treatment with study drug, and 2 weeks of follow up).

The duration for Part D of the study will be variable depending on the study enrollment rate; i.e. the time between enrolling the first and last participant. The minimum duration of participation will be up to 30 weeks for the last participant enrolled (up to 4 weeks of screening, 24 weeks of treatment with study drug, and 2 weeks of follow up) and a maximum of up to 54 weeks for the first participant enrolled (up to 4 weeks of screening, up to 48 weeks of treatment with study drug, and 2 weeks of follow up).

The end of study will commence once the last participant reaches 24 weeks of treatment. At that time, all study participants will complete their next scheduled visit (End of Treatment [EoT]) and the 2 weeks of follow up (End of Study [EoS]).

